11.5.6 Non-Fatal Overdose Questionnaire

Non-fatal overdose is assessed using a single-item question developed and used in prior research.[65] The questionnaire is self-administered using the timeframe of the past 6 months.

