A secondary aim is to evaluate the impact of the STOP intervention on days of alcohol and drug use that increases risk of overdose. For this aim, three variables will be analyzed separately: number of days of binge alcohol use, number of days of benzodiazepine use, and number of days of stimulant use. The analyses will be executed in the same way as the above analyses for days of risky opioid use. Time trend analyses will be executed as described above. Analogous analyses will be performed for another secondary aim, which is to assess impact of STOP on the number of days of marijuana and other drug use (also analyzed separately as two distinct variables), and on the number of days of taking prescribed opioids for symptoms other than for pain and the number of days of taking pain medication belonging to someone else.

Analyses for several Aim 2 secondary outcomes are outlined below. In general, mixed effects regression models with treatment by time interactions (analogous to those described above for the primary outcome) or generalized linear models with generalized estimating equations (GEE) to account for correlation of responses, will be fit. Further details for these models, including distributional assumptions and covariance structure, will be specified in the SAP.

- The incidence of moderate to severe OUD (defined as a score of at least 4 on the CIDI) within 12 months of follow-up will be compared between treatment groups and may be compared for shorter time intervals.
- The proportions of individuals whose average number of days (within 30 days) of illicit or nonmedical opioid use during 180 days of follow-up increased relative to their baseline measure (days of use in the 30 days before the baseline assessment) will be compared between groups at 6 and 12 months.
- Self-reported overdose risk behavior will be measured by the overdose risk behavior questionnaire (which gives a numeric score) at baseline, 6, and 12 months. Mean scores will be compared between groups at 6 and 12 months with regression models.
- The total number of non-fatal opioid-related overdose events in the past 3 months will be measured at baseline, 6, and 12 months. Mean numbers of opioid-related overdose events will be compared between groups.

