2.2.2 Secondary Objectives

The trial has two secondary objectives, which capture patient participant-level and provider-level impacts of the STOP intervention.

The patient-level secondary objective (Aim 2) is to examine the impact of STOP on important patient-level outcomes of substance use that increases opioid-related overdose risk (binge alcohol use, benzodiazepine and stimulant use), other drug use, OUD and other drug and alcohol use disorders, overdose risk behaviors and nonfatal overdose events, pain symptoms and related functioning, mental health symptoms (depression, anxiety, suicidality), sleep, health-related quality of life, and acute health care utilization. We hypothesize that patient participants in the STOP condition, in comparison to participants in the EUC condition, will have:

- H2.1 Fewer days of binge alcohol use.
- H2.2 Fewer days of benzodiazepine use.
- H2.3 Fewer days of stimulant use (cocaine and amphetamine-type stimulants).
- H2.4 Fewer days of marijuana use.
- H2.5 Fewer days of other drug use (not including opioids, benzodiazepines, stimulants, and marijuana).
- H2.6 Lower proportion of individuals having increased days of illicit or nonmedical opioid use.
- H2.7 Reduced prescription opioid misuse behaviors, among patients receiving prescribed opioids.
- H2.8 Lower incidence of moderate-severe OUD.
- H2.9 Lower rates of non-opioid drug use disorder or alcohol use disorder.

- H2.10 Lower rates of self-reported overdose risk behavior and nonfatal opioid-related overdose events.
- H2.11 No worsening of pain symptoms and pain-related functioning.
- H2.12 Fewer symptoms of depression (including suicidality) and anxiety.
- H2.13 Better sleep quality.
- H2.14 Better health-related quality of life.
- H2.15 Lower rates of acute health care utilization (ED and hospital visits).

The provider-level secondary objective (Aim 3) is to characterize the impact of STOP on primary care provider behaviors, including medications prescribed, lab tests, diagnosis of OUD, and frequency of medical visits. Our hypothesis is that providers assigned to the STOP condition, in comparison to providers in EUC, will have, over 12 months of follow-up...

- H3.1 Lower rates of prescribing of high-dose opioids (defined as prescriptions totaling >90 morphine milligram equivalents (MME)) to patients with risky opioid use.
- H3.2 Fewer patients with risky opioid use who are prescribed benzodiazepines.

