 - ii. COMM score, assessed at screening and at 6 and 12 months.
- h. Urine Drug Screens are used to verify self-reported drug use. Urine drug screens are conducted at baseline and at 6 and 12 months.
- i. For participants receiving prescribed opioids, the COMM provides an additional measure of prescription opioid misuse, collected at baseline and at 6 and 12 months.

2. Substance use disorder: Opioid use disorder is assessed at baseline and at 6 and 12 months using the modified World Mental Health Composite International Diagnostic Interview (CIDI). Drug (other than opioid) and alcohol use disorder measures are collected using the PDSQ at baseline and at 6 and 12 months. The PDSQ is used rather than the CIDI for these measures because it is brief and self-administered, which makes it more feasible for these follow-up assessments.
 - a. H2.8. Moderate-severe opioid use disorder (CIDI opioid items)
 - b. H2.9. Drug use disorder (PDSQ drug items)
 - c. H2.9. Alcohol use disorder (PDSQ alcohol items)
3. Overdose risk behaviors and events
 - a. H2.10. Overdose risk behavior and behavioral intention to reduce risk is measured at baseline and at 6 and 12 months (Overdose Risk Behavior Questionnaire)
 - b. H2.10. Episodes of non-fatal overdose are measured at baseline and at 6 and 12 months (Non-Fatal Overdose Questionnaire)
4. Pain symptoms and pain-related functioning
 - a. H2.11. Pain symptoms (severity, impact on functioning) are measured at baseline and at 3, 6, 9, and 12 months using the BPI short form (items #3-6 for pain symptoms and items #9A-9G for functioning).
5. Mental health
 - a. H2.12. Anxiety symptoms are measured at baseline and 6 and 12 months (PROMIS short form)
 - b. H2.12. Depression symptoms and suicidality are measured at baseline and at 6 and 12 months (PHQ-8 and PSS)
 - c. H2.13. Sleep quality is measured at baseline and at 6 and 12 months (PROMIS Sleep 4a)
6. Health-related quality of life and acute health care utilization
 - a. H2.14. Health-related quality of life is measured at baseline and at 6 and 12 months (SF-12)
 - b. H2.15. ED and hospital utilization is measured using participant self-report of acute care events (ED visits, hospitalizations for medical reasons, hospitalizations for detoxification), collected at baseline and at 6 and 12 months.

Measures of provider-level outcomes

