Self-reported overdose risk behavior will be measured by the overdose risk behavior questionnaire (which gives a numeric score) at baseline, 6, and 12 months. Mean scores will be compared between groups at 6 and 12 months in a random-effect regression model. Also, the total number of non-fatal opioid-related overdose events in the past 3 months will be measured at baseline, 6, and 12 months. Mean numbers of opioid-related overdose events will be compared between groups in a random-effect regression model (H 2.10).

Changes in pain-related symptoms and functioning from baseline as measured by the BPI (which calculates a numeric score) will be compared between treatment arms using Mann-Whitney tests. As the scientific goal is to demonstrate no worsening of pain, a noninferiority test will compare changes in BPI score between treatment and control groups with a minimal clinically important difference of 1 based on the IMMPACT recommendations. A secondary analysis will distinguish the effect of STOP on the change in pain-related symptoms for participants with opioid prescriptions at baseline, and the effect for those who were enrolled solely due to illicit use.

Symptoms of depression, suicidality, anxiety (H2.12), and poor sleep (H2.13) in the past two weeks will be measured at baseline and quarterly (PHQ-8) and at baseline, 6, and 12 months (PROMIS anxiety and sleep measures and PSS). Mean values will be compared between treatment arms in random-effect regression models.

Health-related quality of life (H2.14), and ED and hospital utilization (H2.15) in the past two weeks will be measured at baseline and at 6 and 12 months. Mean values will be compared between treatment arms in random-effect regression models.

Similar models will be fit for the Aim 3 objectives, but these will use provider rather than patient as the unit of observation, so will not need a PCP effect to adjust for within-PCP correlation. Regression models will be used to compare number of prescriptions of high-dose opioids within 12 months of follow-up between treatment arms as well as number of days prescribed during 12 months follow-up. Similar analyses will be done for number of prescriptions for any opioids or benzodiazepines, numbers of naloxone kits prescribed, numbers of urine toxicology tests ordered and completed, and number of patient participants receiving a new diagnosis of OUD.

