8.1 Non-fatal Drug or Alcohol Overdoses

The number of patient participant self-reported non-fatal drug or alcohol overdoses in the past 6 months is collected at baseline, 6-months, and 12-months. A non-fatal drug or alcohol overdose is defined as taking too many drugs and/or medications/pills, or drinking too much alcohol, which causes 'poisoning', 'passing out', 'nodding out', 'blacking out', or an 'overdose' or 'OD'.

A summary table of the total number of self-reported non-fatal overdoses, number of patient participants reporting at least one non-fatal overdose as well as the number of non-fatal overdoses reported per patient participant at each visit will be presented by treatment arm. A listing of the number of overdoses reported at each visit for patient participants who have reported at least one overdose at any visit by treatment arm will be provided. The listing will include Site, Participant ID, date of enrollment, visit, date of assessment, number of overdoses, and comments from the Non-Fatal Overdose Questionnaire (NFO).

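### The overdose-event half of H2.10 is analysed as opioid-related events over 3 months, but its questionnaire, as described, counts any drug or alcohol overdose over 6 months

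*SAP*

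**What the plan says.** The hypothesis, in SAP 2.2.2 and in Protocol 5.2 and 14.1.2, is "H2.10 Lower rates of self-reported overdose risk behavior and nonfatal opioid-related overdose events". It has two halves: a risk-behavior score and a count of events. This point concerns only the events.

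For the analysis, Protocol 14.6 says: "The total number of non-fatal opioid-related overdose events in the past 3 months will be measured at baseline, 6, and 12 months". SAP 7.8 carries the sentence over, stating that "the total number of non-fatal opioid-related overdose events in the past 3 months will be measured at baseline, 6, and 12 months", and adds that mean numbers of opioid-related events will be compared between arms in a random-effect regression model.

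The outcome definitions (Protocol 7.2.1 and 14.2.2, SAP 7.7) name the Non-Fatal Overdose Questionnaire as the source of the events, at baseline, 6 and 12 months. They set no opioid restriction and no recall window. Protocol 11.5.6 describes the instrument as a single item: "The questionnaire is self-administered using the timeframe of the past 6 months".

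SAP 8.1, which uses the same questionnaire for safety reporting, describes its content: "A non-fatal drug or alcohol overdose is defined as taking too many drugs and/or medications/pills, or drinking too much alcohol". Passing out and blacking out are among the consequences that qualify. SAP Table 65 and Listing 1 use the same any-substance, 6-month count.

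**The concern.** The analysis sentence differs from the instrument in both event type and recall window. One count of all overdoses over 6 months does not contain a count of opioid overdoses over 3 months, and neither document gives a rule for getting from one to the other.

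Three things follow if the text stands.

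- The lead node, which analyses H2.10 (SAP 1.0, Table 1), would have to settle event type and window with the data in hand.
- If it used the item as collected under the label in SAP 7.8, alcohol episodes could be reported as opioid-related overdoses. Such episodes are plausible here: patients with alcohol use are among those prioritised for prescreening (Protocol 8.2.2), and binge drinking is itself an outcome (H2.1).
- The same answers would appear in the study's reports under two incompatible descriptions, once in the safety tables and once under H2.10.

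**Working it through.** The plan gives no figure for this outcome to reproduce. The check sets the descriptions side by side and then works out what a wrong window would do.

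| Attribute | Analysis text (SAP 7.8, Protocol 14.6) | Instrument (Protocol 11.5.6, SAP 8.1, Table 65, Listing 1) | Agree? |
|---|---|---|---|
| Event type | Opioid-related | Any drug, medication or alcohol | No |
| Recall window | 3 months | 6 months | No |
| Visits | Baseline, 6, 12 months | Baseline, 6, 12 months | Yes |

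**Coverage of follow-up.** A 3-month window at the 6- and 12-month visits covers months 4–6 and 10–12: 3 + 3 = 6 of 12 months, or 50%. A 6-month window at the same visits covers 6 + 6 = 12 of 12 months, or 100%.

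**Effect of the wrong window on a rate.** Let C be a count collected over 6 months. The correct monthly rate is C/6. Read as a 3-month count it becomes C/3, and (C/3)/(C/6) = 2, so the implied rate doubles.

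**Effect of the wrong window on the comparison.** With mean counts S in the STOP arm and E in the EUC arm, (S/3)/(E/3) = (S/6)/(E/6) = S/E. The between-arm ratio does not change.

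**Effect of the wrong event type.** Let f be the opioid share of counted events in the EUC arm, a the STOP/EUC ratio for opioid events, and b the ratio for all other events. The ratio observed on the item is f·a + (1 − f)·b. The documents give none of f, a or b, so the distance between this and a cannot be computed.

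**Other possible sources.** SAP 8.1 shows that the form has a comments field, which might name a substance for some events, but no coding rule is given. Emergency department and hospital records collected by research staff carry diagnoses (Protocol 11.8.3, SAP 8.3 and 8.4). They would catch only overdoses that led to acute care, and they are not the self-report source named for H2.10.

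**A related window error in SAP 7.8.** Emergency department and hospital utilization (H2.15) is given a two-week window. Protocol 11.5.11 says that participants report the past 6 months.

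**The case against.** The strongest reply is that this is a drafting slip with little reach. The outcome definitions already fit the instrument, and the 3-month window sits in one sentence that passed from protocol to SAP. H2.10 is not among the key secondary outcomes: SAP Table 1 gives that label to H2.1–H2.5 and the urine drug screens, and puts H2.10 with the others. Secondary tests carry no multiplicity adjustment and are to be read with that in mind (SAP 9.0). All of this stands, and it limits the weight of the point. It does not reconcile the passages, and the opioid restriction is also in the hypothesis.

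The questionnaire itself is not reproduced, so the claim about event type rests on the SAP's description of it. That also stands. The window mismatch is the firmer half, because Protocol and SAP both state 6 months for the item.

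Four stronger readings are tempting, and the documents do not support them.

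- *Safety reporting is wrong.* It is not: SAP 8.1, Table 65 and Listing 1 state drug or alcohol and 6 months.
- *H2.10 as a whole fails.* The risk-behavior half comes from a separate 9-item questionnaire (Protocol 11.5.5) and is untouched.
- *The wrong window biases the treatment effect.* The ratio is unchanged, as shown above.
- *The opioid effect is diluted by a known amount.* That needs an opioid share and effect sizes that the documents do not give. It is also unsafe to assume no effect on other overdoses, since the trial hypothesises fewer days of binge alcohol, benzodiazepine and stimulant use (H2.1–H2.3), and the coaching also addresses other substances (Protocol 10.6.2).

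**Conclusion.** The contradiction is real and holds in both documents. As described, the item cannot supply the variable that SAP 7.8 and Protocol 14.6 specify. The consequence is one mislabelled secondary outcome. A rate computed on the stated window would be twice the correct one in each arm, with the arm ratio unchanged, and any dilution is of unknown size. The primary outcome and the safety tables are unaffected.

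This assumes that SAP 8.1 and Listing 1 describe the form fully apart from its comments field. If the form does record the substance, the event-type half could be met by stating the derivation. The window half would remain. The H2.15 window is a separate, confirmed error in the same section.

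**What to change.** 1. In SAP 7.8 and Protocol 14.6, change the overdose window from 3 to 6 months.
2. Rename the analysed variable *self-reported non-fatal drug or alcohol overdose (any substance)*.
3. State that the overdose-event part of H2.10, but not the risk-behavior score, cannot be claimed as opioid-specific unless a separate source, or a coding rule for the comments field, is fixed before analysis.
4. Carry the same change to the H2.10 hypothesis text (Protocol 5.2 and 14.1.2, SAP 2.2.2) and to the overdose component of Exploratory Objective 2 (Protocol 5.3 and 14.1.3, SAP 2.2.3 and 7.9), which also calls for opioid-related events.
5. Separately, in SAP 7.8, change the window for H2.15 from two weeks to the 6 months that the form asks about.

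The cost is wording in two documents and a somewhat narrower claim for the event half of H2.10. No new data collection is needed. A coding rule for the comments field, if wanted, would add a small task and would need to be written before the comparison is run.

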2.3.3 Treatment Randomization

This is a cluster-randomized trial in which PCPs are the clusters. In study sites where PCPs practice in teams, randomization will be at the team level (for example, if PCPs practice in teams of two, the two PCPs will be treated as one cluster in the randomization). PCPs will be randomized, stratified by site, in a 1:1 fashion to the STOP or EUC condition.

Patient participants enrolled in the study will receive STOP or EUC according to the assignment of their PCP.

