This table will be repeated by visit and prescription for opioids in the past 6 months (yes/no) as reported on the COMM. The table will present the number and percentage of participants at that visit that reported having an opioid prescription in the past 6 months. If a patient participant does not complete the COMM assessment at that visit, the previous COMM response will be used to determine if the patient participant has an opioid prescription. For example, if the patient participant does not do the 12-month COMM assessment but has a 12-month UDS, the COMM response from the 6-month visit will be used to categorize the participant at the 12-month visit. If

the patient participant does not have any COMM responses from the baseline, 6 or 12-month visits but has UDS collected for those visits, it will be assumed the patient participant does not have an opioid prescription for any of the visits.

The following analysis will be done by the LN:

The proportions of individuals whose average number of days (within 30 days) of illicit or nonmedical opioid use during 180 days of follow-up increased relative to their baseline measure (days of use in the 30 days before the baseline assessment, H2.6) will be compared between groups at 6 months and 12 months using chi-square test respectively.

Descriptive summary statistics for COMM score assessed at screening and at 6 and 12 months (H2.7 h), Comparisons of the secondary outcomes between the two treatment arms will be conducted using t-tests or Mann-Whitney tests for continuous measures, chi-square tests for categorical measures.

Generalized estimating equations (GEE) to account for correlation of responses within PCP cluster will be fit for the incidence of moderate to severe OUD (defined as a score of at least 4 on the CIDI, H2.8) and drug use disorder (PDSQ drug items, H2.9) and alcohol use disorder (PDSQ alcohol items, H2.9) assessed at 6 and 12 months separately. Treatment effect is estimated adjusting for baseline level of each measurement. Time trend is evaluated using a time variable.

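### SAP 7.8 tests BPI pain change (and H2.6, apparently COMM) without PCP cluster or site, and gives the pain noninferiority test no model or interval

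*SAP*

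**What the plan says.** SAP 2.3.3 states that "PCPs will be randomized, stratified by site, in a 1:1 fashion to the STOP or EUC condition"; PCPs who work in a team form one cluster. For the Aim 2 patient outcomes, Protocol 14.6 says "In general, mixed effects regression models with treatment by time interactions (analogous to those described above for the primary outcome", with GEE as the alternative, and leaves distributions and covariance to the SAP. Its list includes H2.6, the BPI and COMM.

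SAP 7.8 then assigns methods unevenly:

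- **H2.8 and H2.9:** "Generalized estimating equations (GEE) to account for correlation of responses within PCP cluster will be fit".
- **H2.12 to H2.15:** "Mean values will be compared between treatment arms in random-effect regression models". H2.10 is treated similarly.
- **H2.11, BPI change:** "as measured by the BPI (which calculates a numeric score) will be compared between treatment arms using Mann-Whitney tests". A separate sentence adds that "a noninferiority test will compare changes in BPI score between treatment and control groups with a minimal clinically important difference of 1".
- **H2.6, increased opioid use:** the proportions "will be compared between groups at 6 months and 12 months using chi-square test respectively".
- **COMM:** "Descriptive summary statistics for COMM score assessed at screening and at 6 and 12 months (H2.7 h), Comparisons of the secondary outcomes" runs on into a general statement of t, Mann-Whitney and chi-square tests. The reader cannot tell which outcomes it covers.

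SAP 9.0 sets a two-sided 5% level for the primary outcome only and promises, in general terms, intervals with effect estimates.

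**The concern.** Tests that treat patients as independent do not match a design that randomizes PCPs within site. Their error rate rises above nominal to the extent that PCPs in the same site differ in the quantity tested. It falls below nominal to the extent that the correlation lies between sites, because stratification balances sites while the tests leave site variation in the error term. The level therefore depends on unknown quantities. A PCP effect that is stable over time cancels from a change score, so for BPI change and H2.6 what counts is clustering in the change.

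No worsening of pain is a stated hypothesis, and the protocol itself recognises that the intervention may lead to less opioid prescribing. A Mann-Whitney test gives no interval for a mean difference to set against 1 point. If the unstated interval ignored within-site PCP clustering it would be too narrow, which favours a claim of noninferiority.

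**Working it through.** **Inputs.** About 60 PCPs with patients and 5 patients each (Protocol 2.1.2), 20% loss (SAP 10.0) and 5 sites: 60 × 5 × 0.8 = 240 analysed, taken as 5 sites × 12 PCPs × 4 patients, or 120 per arm. The ICC ρ (total within-PCP correlation) and the share f of it that lies between sites are assumptions; the documents give neither for these outcomes.

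**The plan's own clustering figure.** SAP 10.0 puts the middle half of PCP-specific control means at 17 to 25 days per 90, from logit variances of 0.15 (PCP) and 0.25 (patient). Simulating those variances gives 17.0 and 25.1, so the figure reproduces. The implied ICC of the 180-day count is about 0.34. That is the level of a different outcome, not pain change, and is not used for the BPI.

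**Ratio R of true to naive standard error of the arm difference.** Site cancels from the true variance but stays in the naive one:

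R² = [(1−ρ) + 4(1−f)ρ] / [(1−ρ) + 0.9748(1−f)ρ + 0.8067fρ]

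where 0.9748 = (120/119)(29/30) and 0.8067 = (120/119)(4/5). At ρ = 0.10:

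- f = 0: 1.30/0.9975, R = 1.142
- f = 0.5: 1.10/0.9891, R = 1.055
- f = 1: 0.90/0.9807, R = 0.958

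R = 1 when 3.0252(1−f) = 0.8067f, that is f = 0.789. ρ drops out.

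**Mann-Whitney error, two-sided nominal 5%.** Site-stratified 1:1 randomization, normal outcome, no effect, 40,000 trials per setting (Monte Carlo SE √(0.05×0.95/40,000) = 0.11 points):

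| Share between sites | ICC 0.05 | ICC 0.10 | ICC 0.20 |
|---|---|---|---|
| 0 | 6.8% | 8.3% | 11.6% |
| 0.25 | 6.1% | 7.4% | 9.8% |
| 0.5 | 5.7% | 6.2% | 7.8% |
| 0.75 | 4.95% | 5.1% | 5.5% |
| 1 | 4.6% | 4.2% | 3.3% |

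At ICC 0.01 every value is 4.8 to 5.3%. A site-adjusted analysis of PCP means (t, 54 df) stays at 4.80 to 5.23% in all 20 settings.

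**H2.6.** Baseline binomial(30), follow-up binomial(180), mean 20/90, the SAP's variances, 8,000 trials. With stable PCP effects the chi-square error is 4.2%. With an added, assumed PCP variance in change of 0.05 or 0.15 it is 8.3% or 13.2%, or 5.9% or 8.2% if half of that is between sites.

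**COMM.** Protocol 8.2.2 expects 15 to 20% of patients to be on prescribed opioids: 240 × 0.15 = 36 to 240 × 0.20 = 48 analysed, with a size-weighted 1.48 to 1.64 per PCP. At ICC 0.05 the error is 5.3 to 5.4% (f = 0) or 4.9 to 5.0% (f = 0.5).

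**Pain noninferiority.** If the interval ignored clustering, and the level were one-sided 2.5% (both assumptions), false claims at a true difference equal to the margin would be 3.3 / 4.3 / 6.1% (f = 0), 3.0 / 3.2 / 4.0% (f = 0.5) and 2.3 / 2.2 / 1.6% (f = 1) at ICC 0.05 / 0.10 / 0.20. Separately, SAP 3.4 defines two BPI scores and SAP 7.7 lists four follow-up visits: 2 × 4 = 8 tests fit the text.

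**The case against.** The strongest case against runs as follows.

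- **Size.** A change score may have a very small ICC, and at 0.01 nothing is inflated. H2.6 shows no inflation under the SAP's own variances, and COMM none that matters. This stands: the size is conditional, and the material case is BPI.
- **The noninferiority test is silent, not wrong.** The Mann-Whitney sentence is separate, and Protocol 14.6 supplies mixed models or GEE as a default. This stands in part: the error rates above are hypothetical and the sure defect is under-specification. But neither the protocol default nor the general interval statement in SAP 9.0 fixes the level, score or visit.
- **Site is missing elsewhere too.** The GEE text for H2.8 and H2.9 names PCP cluster and baseline but not site. This is true, so the PCP term, not site, is what sets BPI, H2.6 and COMM apart.
- **No 5% level is claimed for secondary outcomes, and the protocol says only in general.** Both are true, but p-values will be reported and read, and the SAP gives no reason for the exception.
- **Approximations.** The 79% break-even assumes exactly 4 patients in every PCP. The COMM count may be low, because COMM goes to anyone reporting an opioid prescription in the past 6 months; more patients per PCP would move COMM towards the BPI figures.
- **A cluster-adjusted rank test would also work.** It would for the comparison, but it gives no mean-difference interval for the margin.

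**Conclusion.** The concern holds. For BPI change and H2.6, SAP 7.8 names tests that ignore the unit of randomization. They depart from the protocol's general rule and from the SAP's own handling of neighbouring outcomes; COMM apparently shares the problem. For BPI change the error exceeds 5% unless roughly four fifths of the correlation lies between sites. It is negligible at ICC 0.01 and reaches 11.6% at ICC 0.20 with all correlation within site. The ICCs and site shares are assumptions. The noninferiority gap needs no such assumption: as written, no single prespecified test supports a claim that pain did not worsen.

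These are secondary outcomes outside the key set and are analysed by the lead node. The primary model has a random PCP intercept and a site effect, so the main result is untouched. The point should be fixed, but it does not threaten the trial's principal conclusion.

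**What to change.** Amend SAP 7.8 as follows:

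1. Analyse BPI change, H2.6 and COMM by GEE or a mixed model with PCP cluster, adjusted for site and the baseline value: linear for BPI change and COMM, logistic for H2.6. Use a small-sample standard-error correction for COMM, given about 36 to 48 expected patients.
2. Declare noninferiority on pain only if the upper limit of the cluster-adjusted 95% confidence interval for STOP minus EUC in BPI change is below 1. Name the BPI score and the visit to which the margin applies.
3. Rewrite the COMM sentence and list the outcomes it covers.
4. Have the lead node name its software, since SAP 13.0 names analysis software only for the DSC.

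The cost is a documented amendment, because version 2.0 is already approved, and no new data. That version already adds a post hoc analysis, so the amendment should record its timing and whether results had been seen. Relative to unadjusted intervals at ICC 0.05 / 0.10 / 0.20, the adjusted ones are 7 / 14 / 27% wider if all correlation is within site, 3 / 5.5 / 11% wider if half is between sites, and 2 / 4 / 9% narrower if all is.
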